4. STUDY DESIGN, AIMS AND OBJECTIVES

4.1. Study Design

The study is a Prospective Pragmatic Cohort Study with a before-and-after study design

4.2. Study Aim

The overarching aim of the TRiAD study is to evaluate the effectiveness, operational feasibility, acceptability, and cost-effectiveness of implementing the Xpert MTB/XDR for rapid triage and selection of all-oral regimens for DR-TB.

4.3. Primary Objectives:

- To compare the time to initiation of resistance-pattern appropriate TB treatment from the date of first sputum collection with the standard of care compared to a historical cohort, stratified by geographical location
- To assess the proportion of DR-TB participants with cure and/or DR-TB treatment completion at month 12 compared to a historical control group

4.4. Secondary Objectives:

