2.3. Evidence for novel regimens and diagnostics proposed in this study

2.3.1. Novel, all-oral treatment regimens for DR-TB

Historically, MDR-TB and XDR-TB patients have been treated with a multi-drug treatment regimen which comprises of an intensive phase of treatment of 8 months and a total duration of treatment of 20-24 months. For patients with RR-TB or MDR-TB who were not previously treated with second-line drugs and for whom resistance to fluoroquinolones and second-line injectable agents was excluded or is considered highly unlikely, a shorter treatment regimen (STR) still including an injectable, was recommended. This STR was evaluated in Stage 1 of the STREAM trial and is composed of high-dose later generation fluoroquinolone, clofazimine, pyrazinamide and ethambutol throughout, supplemented by amikacin, prothionamide, and high-dose isoniazid in the intensive phase. The treatment duration of the intensive phase is four months (extended to a maximum of six months until sputum smear conversion), and the duration of the continuation phase is five months. In December 2019, WHO issued a rapid communication encouraging countries to replace the injectable in this regimen with BDQ and use the all oral bedaquiline based STR as the preferred option.

In addition to this newly recommended shorter all-oral MDR-TB regimen, there are other shorter regimens currently being evaluated in clinical trials for the same and different patient groups. Many of these regimens employ new or repurposed medicines, which have been shown to be effective in clinical trials. These regimens have common desirable features: good tolerability, all-oral and with shorter treatment duration.

One such regimen is the BPaL regimen which consists of BDQ, pretomanid and linezolid given for 6 months. Currently, the BPaL regimen is the most appropriate alternative for the treatment of pre-XDR TB (MDR with additional fluoroquinolone resistance) and XDR-TB (pre-XDR with resistance to at least one additional Group A drug). The efficacy of the regimen was evaluated

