5. STUDY INTERVENTION

There are 3 study interventions:

1. The Xpert MTB/XDR assay will be used as a diagnostic adjunct to any currently available Nucleic Acid Amplification Tests for drug-resistance detection changes to screen participants. The Xpert MTB/XDR assay will enable prompt identification of the following DR-TB participant categories:
 - a. HR-TB
 - b. Rif mono-resistant TB
 - c. MDR-TB
 - d. Additional fluoroquinolone (FQ) resistance, i.e., pre- XDR TB
2. Early initiation of the most appropriate, evidence-based DR-TB regimen. This will be guided by the TB resistance pattern categorization from the Xpert MTB/XDR diagnostic.

Choice of DR- TB regimen will be determined by:

- a. Best available evidence generated from use of novel regimens as they become available, or
 - b. Current WHO and in-country guidelines (Table 2).
3. In parallel, the TB-MBLA will be used to provide real-time bacillary load monitoring over the course of treatment to assess response to treatment.

Table 2: Current Drug-Resistant TB Treatment Regimen by TB resistance profile and proposed study approach

Current Guidelines on DR- TB treatment	Regimen class	Current Recommended Regimen with Duration (months) by Drug resistance profile per participating country	Proposed All-oral regimen [#]
	HR-TB	RHZE + Lfx (6)	RHZE + Lfx (6) [#]
RR-TB and MDR-TB Short- Course Regimen		
All oral regimen:
 
SA: (4-6)BDQ-Lfx (or MXF)- LZD, INHhd-CFZ-E-Z/ (5) LFX-CFZ-E-Z Nigeria: (4-6)BDQ-MFX-HH-PTO-CFZ-E-Z/ (5)BDQ (2) MFX-CFZ-E-Z Ethiopia:(4-6)AM-MFX-CFZ-HH-PTO-E-Z/ (5)MFX-CFZ-E-Z
 
or
 
Injection-based regimen:
 
(4)AMK-MFX-CFZ- INHhd -PTO-E-Z/(5) MFX-CFZ-E-Z
	BDQ based all-oral regimen [#]
RR-TB; MDR-TB; and PreXDR-TB (Second-line resistance) Long all-oral Regimen* :		
SA: (6)BDQ-LFX-CFZ-LZD/(12)LFX-CFZ- LZD Nigeria: (6)BDQ-MFX-CFZ-LZD/ (12) MFX- CFZ-LZD Ethiopia: (6) BDQ-LFX-LZD-CFZ-CS/(14) LFX- LZD-CFZ-CS
	BPaL [#]
PreXDR-TB (FQ resistance) and XDR-TB# Long Individualised Regimen*:		
SA: (6-8)BDQ-CFZ-LZD-DLM-TRD/(12)CFZ-LZD-TRD-Z- INHhd Nigeria: (6)BDQ-CFZ-LZD-CS/ (12)CFZ-LZD- CS Ethiopia: (BDQ)-(LFX)- (MFX)-(LZD)-(CFZ)-(CS)- (DLM)-(PTO)-(Z)-(AM)-(S)-(PAS)
	BPaL [#]

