Abbreviations: HR-TB, Isoniazid Mono-Resistant TB; RR-TB, Rifampicin-Resistant TB; MDR-TB, Multi Drug-Resistant TB; XDR, Extensively Drug-resistant TB, SA, South Africa, LFX, levofloxacin; BDQ, Bedaquiline; MXF, moxifloxacin; LZD, linezolid, INHhd, high-dose isoniazid; CFZ, clofazimine; E, ethambutol; Z, pyrazinamide; PTO, protonamide; DLM, Delamanid; TRD, Terizidone, BPaMz, Bedaquiline -Pretomanid-Moxifloxacin-Pyrazinamide ; BPaL, Bedaquiline -Pretomanid-Linezolid

* Longer regimens recommended when the construction of MDR/RR-TB regimen with 3 group A and 2 group B drugs is not possible due to intolerance to the medicines, acquired additional resistance etc.

Regimen selection based on WHO approved all-oral regimen or the best available evidence-based regimen; once results for proposed BPaMz and ZeNIX Formal amendments will be submitted for review upon consideration of additional regimens for the use in the study

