6.2.3. Selection of Historical Cohorts

Each CRS will build a dataset of historical RR-TB participants that were diagnosed and started on treatment within 12 - 18 months prior to starting enrolment of the study at each of the clinical research sites. Clinical and laboratory data from this retrospective cohort will be obtained from treatment registers, participant charts and laboratory databases at each of the clinical research sites. The following data variables will be extracted: date of birth, or age, sex, HIV and ART status, facility or clinic, year and month of treatment, type of DR-TB, certainty of diagnosis (confirmed by DST or presumed, i.e., contact of DR-TB source case or failing adherent first-line TB treatment), disease classification, treatment start date and any bacteriological results on treatment (date, mycobacterial culture, DST and genotypic results), where relevant. Data on all drugs from previous DR-TB treatment regimen, DR-TB Outcomes: cure, completion, default, death, loss to follow up (LTFU) will be abstracted. Historical data will be collected on specially designed case report forms (CRF) and will be subject to routine quality assurance/control QA/QC of data to ensure maximum quality. Bias by time period and by other confounders such as HIV, gender and age, will be controlled for in the analysis. No historical data will be generated for cohort 2, as no routine data on HR-TB is available.

6.3. Participant Inclusion Criteria for cohorts 1 and 2

1. Ambulant adults \geq 18 years of age
2. Newly diagnosed PTB patients receiving less than 5 days of treatment since new diagnosis:
 - a) Cohort 1: < 5 days of DR-TB treatment
 - b) Cohort 2: < 5 days of INH mono-resistant TB treatment preceding study entry for the current TB episode, or
3. Sputum positive (smear and or culture) TB patients classified as failing first line treatment
4. Any currently available Nucleic Acid Amplification Tests for drug-resistance detection changes/assay positive for M.tb infection with:
Cohort 1: at least Rifampicin resistance

- Cohort 2: Rifampicin susceptible co-occurring with INH, fluoroquinolone, ethionamide or aminoglycoside resistance (detected by Xpert XDR) occurring alone or in combination
5. Capacity to provide informed consent
 6. HIV infected and uninfected participants are allowed in the study. Participants already on ART will be allowed in the study provided the ART regimen in use has no contraindications to the proposed TB drug regimen

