Participants will be scheduled to undergo appropriate evaluation at baseline, during and after treatment. Study visits will occur at week 2, monthly for the duration of DR-TB treatment and 3-monthly following completion of treatment where allowable within the study's operational time frame. Participants on short-regimen will be seen for a maximum of 3 post-TB treatment visits, 3 months apart (Table 3). Active follow-up will occur for the duration of TB treatment and passively thereafter, for a maximum of 18 months after study enrolment. Participants who receive long treatment regimens will be actively followed-up for the duration of the intensive phase of treatment and passively thereafter to obtain an end-of-treatment outcome. Research-specific activities during follow-up include assessment of clinical and microbiological response to treatment, solicitation and reporting of adverse events and serious adverse events, administration of study specific questionnaires related to costs, acceptability and feasibility of the intervention. Passive follow-up will be conducted telephonically or through NTP registers to assess rates of relapse after TB treatment completion. Study related specimen collection will occur at baseline (enrolment) and at all follow-up visits. Baseline sputum samples will be collected for Xpert MTB/XDR testing, pDST, WGS, and TB-MBLA testing. Follow-up sputum samples will be collected for routine culture and susceptibility testing and sputum storage for batched TB-MBLA testing.

Evaluations for Cohort 2:

Participants will be referred to the NTP and will not undergo further active follow-up within the study (table 4). Treatment outcomes for these participants will be monitored passively through monthly telephonic monitoring or through routinely collected outcome data within the national TB program until 15 months after enrolment.

Table 3: Schedule of Evaluation for Drug-Resistant Tuberculosis participants in the TRiAD Study Cohort 1

Visit	Screening	Enrolment	24h after 1 st treatment dose	Treatment and Follow Up Period ^a											
				Week 2	Month 1	Month 2	Month 3	Month 4	Month 5	Month 6	Month 9	Month 12	Month 15	Month 18	
Time of visit															
Inclusion/Exclusion Criteria	X	X													
Informed Consent	X	X													
Storage informed consent ^g		X													
Sociodemographic Information		X													
Medical/treatment History ^b		X													
Clinical Exam ^c		X		X	X	X	X	X	X	X	X	X	X	X	X

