9.3. Outcome Status

Outcomes are based on WHO's reporting framework for tuberculosis in 2020 (39).Treatment outcome definitions have recently been revised by WHO and will be updated in the 2021 revision of WHO's *Definitions and reporting framework for tuberculosis*. Once this guideline becomes available and the new definitions are adopted for programmatic implementation, the protocol will be updated (<https://www.who.int/publications/i/item/9789240022195>).

Table 7: Treatment outcomes for RR-TB/MDR-TB/XDR-TB participants treated

Outcome	Definitions per TRiAD Protocol	2021/2022 WHO Definitions
Cured	Treatment completed as recommended by the national policy without evidence of failure AND three or more consecutive cultures taken at least 30 days apart are negative after the intensive phase	A pulmonary patient with bacteriologically confirmed DR-TB at the beginning of treatment who completed the recommended treatment , with evidence of bacteriological response* and no evidence of failure
Treatment completed	Treatment completed as recommended by the national policy without evidence of failure BUT no record that three or more consecutive cultures taken at least 30 days apart are negative after the intensive phase	A patient who completed treatment as recommended and who does not meet the definition of cure or treatment failure
Treatment failed *	Treatment terminated or need for permanent regimen change of at least two anti-TB drugs because of: 
 - lack of conversion by the end of the intensive phase, or - bacteriological reversion in the continuation phase after conversion to negative, or - evidence of additional acquired resistance to fluoroquinolones or second-line injectable drugs, or - adverse drug reactions (ADRs) 	A patient whose treatment regimen needed to be terminated or permanently changed to new regimen or treatment strategy. Reasons for change include : 
 - No clinical and or bacteriological response - Adverse drug reaction/s - Evidence of additional drug resistance to medicines in the regimen
Died	A participant who dies for any reason during the course of treatment.	A patient who died for any reason during treatment
Lost to follow-up	A participant whose treatment was interrupted for 2 consecutive months or more.	A patient with treatment interrupted for ≥ 2 consecutive months for any reason without medical approval

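### Primary endpoint 2 has two incompatible timings: the objective counts cure or completion at month 12, while the definitions, follow-up and planning rates are end-of-treatment

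*Protocol*

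**What the plan says.** **Objective.** Section 4.3, repeated in Table 1, reads: "To assess the proportion of DR-TB participants with cure and/or DR-TB treatment completion at month 12 compared to a historical control group".

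**Outcome measure and analysis.** Section 4.5 refers to the outcomes of section 9.3. Section 9.2 uses WHO cure or completion in cohort 1 and the same proportion in the historical cohort. Neither gives a month.

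**Definition.** In the protocol column of Table 7, both favourable categories start from "Treatment completed as recommended by the national policy without evidence of failure". The WHO column beside it also requires completion.

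**Follow-up.** Section 7.1 follows long-regimen participants actively through the intensive phase and "passively thereafter to obtain an end-of-treatment outcome". For the historical cohort, section 6.2.3 says "DR-TB Outcomes: cure, completion, default, death, loss to follow up (LTFU) will be abstracted", with no month-12 cut.

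**Regimen length.** Table 2's column of current regimens includes "Ethiopia: (6) BDQ-LFX-LZD-CFZ-CS/(14) LFX- LZD-CFZ-CS" and "SA: (6-8)BDQ-CFZ-LZD-DLM-TRD/(12)CFZ-LZD-TRD-Z- INHhd". Its footnote restricts their use: "Longer regimens recommended when the construction of MDR/RR-TB regimen with 3 group A and 2 group B drugs is not possible". Section 2.3.1 describes older practice as "a total duration of treatment of 20-24 months".

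**Planning rates.** Section 9.1 uses treatment completion proportions from KwaZulu-Natal: 63% on average, 57% on the long regimen and 74% on a bedaquiline-based short regimen. It plans to detect 74% against 85%.

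**The concern.** One primary endpoint is timed in two ways. Under the objective, a patient who is responding well in month 12 of an 18-month regimen is not a success. Under the rest of the protocol, that patient is classified when the regimen ends.

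The difference matters because the comparison is with non-randomised historical controls, and regimen length is expected to differ between the cohorts. Table 2 proposes BPaL, described in 2.3.1 as a 6-month regimen, in the rows where programmes now use the long regimens. A month-12 count would then mix treatment success with treatment length. If month 12 were applied to cohort 1 alone, with final outcomes taken from the registers for controls, the distortion would run the other way.

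**Working it through.** **1. Can month 12 be reached?** Lengths from Table 2, in months:

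| Current regimen | Sum | Length |
|---|---|---|
| Short course, all countries | (4 to 6) + 5 | 9 to 11 |
| Long all-oral, South Africa and Nigeria | 6 + 12 | 18 |
| Long all-oral, Ethiopia | 6 + 14 | 20 |
| Individualised, South Africa | (6 to 8) + 12 | 18 to 20 |
| Individualised, Nigeria | 6 + 12 | 18 |
| Individualised, Ethiopia | not stated | not stated |

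Short courses can end by month 12. The long regimens with a stated length end 6 to 8 months after it, so success at month 12 on them is zero by definition.

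**2. Which timing does the sample size use?** If the 63% average is a mix of the 57% and 74% groups only (an assumption), the implied long-regimen share is (74 − 63)/(74 − 57) = 11/17 = 64.7%. A month-12 count of the same patients, with those still on treatment as non-successes, would give (1 − 0.647) × 74% = 26.1%, not 63%. The planning rates are therefore end-of-treatment rates.

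The stated power is roughly reproducible on those rates. Alpha is not stated; two-sided 5% is assumed. With 220 historical patients against 187 in cohort 1 (220 × 0.85), power for 74% against 85% is 78.2%; with 220 against 220 it is 81.8%. For 71% against 85% at 90% power, 182/0.85 gives 215 per group.

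**3. What could the timing do to the comparison?** Illustration only. Let *s*L = 57% and *s*S = 74% in both cohorts, and let *p*H and *p*1 be the long-regimen shares in the historical cohort and cohort 1. The shares are assumed, because the protocol gives none.

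If patients still on treatment count as non-successes:

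- Month-12 difference = (*p*H − *p*1) × *s*S
- End-of-treatment difference = (*p*H − *p*1) × (*s*S − *s*L)
- Shift = (*p*H − *p*1) × *s*L

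Results:

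- Gap of 10 points: 0.10 × 57 = 5.7 points towards the intervention.
- Gap of 20 points: 0.20 × 57 = 11.4 points towards the intervention.
- Gap equal to the planned 11 points: 0.11/0.57 = 19.3 percentage points.

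**4. Is the direction fixed?** No. Take *p*H = 20% and *p*1 = 0, where the historical end-of-treatment rate is 0.8 × 74 + 0.2 × 57 = 70.6%.

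- Patients still on treatment dropped, earlier failures kept: the historical rate is 59.2/88.6 = 66.8%, a shift of +3.8 points.
- All long-regimen patients dropped: the historical rate is 74.0%, a shift of −3.4 points.
- Month 12 in cohort 1 only, with 10% on long regimens there and those still on treatment as non-successes: −5.7 points.

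**The case against.** **The month-12 phrase may be a stray one.** The outcome measure, the analysis section and the planning rates all point to final outcomes, so the analysts may never apply it. That is plausible, and it is why the repair is cheap. It does not remove the conflict, because the phrase stands in a primary objective, in two places.

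**Long regimens may be rare.** They sit in Table 2's column of current regimens, BPaL is proposed for those rows, and the footnote limits their use. This stands. A reader might infer that the study's proposed regimens run 18 to 20 months, or that the primary result is biased towards the intervention by about its planned effect. The documents support neither. They do show that long regimens are foreseen: 7.1 provides for such participants in cohort 1, section 8.2 allows a switch to an individualised regimen, and the historical controls were treated under programme regimens.

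**Being successfully finished by month 12 is a defensible pragmatic endpoint**, since shorter treatment is part of the intervention. This stands in principle. But that endpoint would need its own definition, a status for patients still on treatment, and planning rates to match. The protocol has none of these.

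**Table 7's note gives an 8-month cut-off.** It says when the outcome criteria start to apply to certain regimens. It does not waive completion.

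**The analysis plan could settle the counting rule.** It could. It should not have to choose between two timings that the protocol itself states.

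**Conclusion.** This is an internal inconsistency in the timing of a primary endpoint, and it should be fixed. Taken as written, the objective makes every patient on an 18- to 20-month regimen a non-success or unclassified at month 12, whatever the response to treatment. Such patients are likelier among the controls.

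Neither size nor direction can be established. The 5.7- and 11.4-point figures rest on three assumptions: the KwaZulu-Natal rates hold at all sites, the long-regimen shares differ by 10 or 20 points, and patients still on treatment count as non-successes. Other counting rules give smaller shifts or reverse the sign. The figures show only that the choice of timing could matter on the scale of the planned difference. No view is taken on which regimen or duration is right.

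**What to change.** 1. Delete the month-12 phrase from section 4.3 and Table 1, so that the objective agrees with 4.5, 7.1, 9.1 and 9.2.
2. Define the endpoint in both cohorts as the final treatment outcome: cured plus completed, over all who started treatment. Use one Table 7 definition column and one ascertainment rule.
3. Label any result for this endpoint at the interim analysis in 9.2 as provisional.
4. Add a month-12 sensitivity analysis, applied identically to both cohorts, with still on treatment as its own category.
5. Make the final outcome observable in cohort 1. The 18-month follow-up limit runs from treatment initiation in 6.2.1, from enrolment in 7.1 and from the end of treatment in Table 3 note a. Give it one origin, and let passive register checks continue until the regimen ends.
6. Reconcile the historical window, which is 12 to 18 months in 6.2.3 and about 24 months in Table 1 and the summary footnotes. Abstract outcomes only once those regimens could have ended. If controls started 12 to 18 months before enrolment opened, a 20-month regimen ends 2 to 8 months after it opens (20 − 18 and 20 − 12). If the window runs up to the start of enrolment, the wait may be about 20 months.

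**Cost.** A protocol amendment and longer passive follow-up for a minority. For a 20-month regimen, the last cohort 1 outcomes arrive 32 to 38 months after first enrolment (12 + 20 and 18 + 20). That fits the 48-month study if enrolment starts near study start, which is an assumption. It is a lower bound, because one Table 2 regimen has no stated length and 8.2 allows extension. Final outcomes also compare unequal risk windows for death and loss, about 6 months against 18 to 20; the sensitivity analysis makes that visible.

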4.4.1. Clinical

- To assess the safety and effectiveness of all-oral regimens under operational conditions.
- To assess all-cause mortality at month 12 and 18, rates of drug/regimen discontinuation for safety concerns, rates of drug-related adverse events

4.4.2. Microbiological

- To assess time to culture conversion, cure, and rates of clinical TB relapse
- To determine the prevalence of HR-TB stratified by geographic location
- To determine the prevalence of pre-XDR and XDR-TB using phenotypic DST to bedaquiline, pretomanid and linezolid
- To determine the proportion of participants with bedaquiline and linezolid resistance warranting a switch from short-course treatment
- To assess the clinical utility of the TB Molecular Bacterial Load Assay (TB-MBLA) as a predictor of treatment outcome
- To assess the diagnostic and clinical performance of the test and triage approach by geographic location using whole genome sequencing (WGS) and Minimum Inhibitory Concentration (MIC) analysis
- To determine the phylogenetic structure and full drug resistance patterns of study samples, including bedaquiline, linezolid, levofloxacin and pretomanid

4.4.3. Cost-effectiveness, feasibility and acceptability compared to the standard of care

- To determine cost per person tested and incremental cost per DR-TB participant timely initiated on the resistance- pattern appropriate regimen
- To determine the incremental cost per DALY averted and per day delay averted in treatment with the resistance- pattern appropriate regimen
- To assess programmatic cost-effectiveness, feasibility, and acceptability of implementing any currently available Nucleic Acid Amplification Tests for drug-resistance detection changeswith Xpert MTB/XDR testing for HR and second-line DR-TB drugs
- To investigate participant's, health care provider's and policy-maker's acceptability of the triage and treat approach
- To assess the feasibility of the implementation of the triage and treat approach in routine care

